5.2. Safety Analysis Sets

The SAF will consist of all enrolled subjects except for the following subjects.

- Subjects who did not take the investigational product at all
- Subjects for whom absolutely no safety data are available following immunization with the investigational product

6. HANDLING OF DATA

6.1. Handling of Missing Values

If a value cannot be measured or is the reference value because of, for example, the assessment was not performed, the test value was missing, or there was a problem with the test sample, this parameter will be handled as a missing value.

6.2. Allowable Assessment Time Point Deviation Window

For the tabulation at each time point of test and observation parameters, data meeting the allowable time window in days specified in “9.1 Test/Observation Schedule” of the study protocol will be used, and data will not be replaced using data from outside the allowable windows.

6.3. Handling of Antibody Titer Data Below the Limit of Quantitation

For the calculation of the descriptive statistics, if the measured antibody titer is below the limit of quantitation, then it will be treated as being the lower limit of quantitation divided by 2.

6.4. Handling of Adverse Event Data When There Are Multiple Events in the Same Period

If the same PT occurs in the same subject occurs multiple times in the period in question (e.g., the safety assessment period or the specified period for each number of doses), then these will only be counted as a single event.

7. STATISTICAL METHODS

7.1. General Methods

7.1.1. Significance Level and Confidence Coefficient

Since this study is an exploratory study, no significance levels have been established. The confidence intervals will be two-sided confidence intervals, and the confidence coefficient will be 95%.

7.1.2. Descriptive Statistics

Unless otherwise specified, the descriptive statistics shown in the following table will be calculated, depending on the type of the data.

Table 7.1.2: Descriptive Statistics

Data Category	Descriptive Statistics
Categorization/Sequential	Numbers and proportions of subjects
Continuous	Numbers of subjects, mean values, SDs, minimums, maximums, medians

7.1.3. Confidence Intervals (e.g., Seroprotection rate, Incidence)

When calculating the confidence intervals for the incidences of adverse events, etc., or the antibody seroprotection rates, Clopper & Pearson method will be used.

7.1.4. Number of Display Digits

The number of digits displayed will be as follows. Additionally, the digits after the number of display digits will be rounded off (or up), except for the minimum and maximum values.

Table 7.1.4: Number of Display Digits

Descriptive Statistics	Number of Display Digits
Number of subjects	Integers
Proportions	Values rounded off to 1 decimal place
Minimum and maximum values	Same as the number of digits of the original variable
Means, standard deviations, and medians	Number of digits of the original variable + 1

7.1.5. Display of Treatment Groups

The display of the treatment groups will be handled as shown in the following table.

Table 7.1.5: Treatment Groups

Treatment Groups	Display
BK1310 0.5 mL per dose	BK1310

7.1.6. Tabulation Time Points and Baselines

The tabulation time points will be displayed as shown in the table below. The baseline will be “Before the first dose at Visit 1.”

Table 7.1.5: Tabulation Time Points

Notation for Tabulation		Assessment Time Points in the Protocol
Assessment Time Point	Abbreviation	
Before the first vaccination	V1	Before the first dose at Visit 1
4 weeks after the primary immunization	V4	Postdose examination 1 at Visit 4
Before the boosterimmunization	V5	Before the fourth dose at Visit 5
4 weeks after the booster immunization	V6	Postdose examination 2 at Visit 6

7.2. Subject Disposition

7.2.1. Analysis Population Eligibility

Analysis population(s): Enrolled subjects

Analysis parameter: Eligibility for the FAS/safety analysis set (included, not included)

Analysis method: For each analysis parameter, the numbers and proportions of subjects will be calculated.

7.2.2. Disposition of Discontinued Subjects

Analysis population(s): Enrolled subjects

Analysis parameter: Discontinued or completion after the vaccination with the investigational product, reason for discontinuation

Analysis method: The number and proportion of subjects discontinuing or completing will be calculated.

Additionally, for subjects discontinuing, the numbers of subjects for each reason for discontinuation will be output.

7.3. Demographic and Other Baseline Characteristics

Analysis population(s): FAS, safety analysis set

Analysis parameter: See Table 7.3

Analysis method: For each parameter, the number and proportion of subjects will be calculated for discrete data, and descriptive statistics will be calculated for continuous data. Additionally, if the FAS and the safety analysis set are the same, only the figures for the FAS will be output.

Table 7.3: Demographic and Other Baseline Characteristics/Analysis Parameters

Analysis Parameter		Data Category
Sex	Male, Female	Discrete
Age in months		Continuous
	≥ 2 and < 3 months, ≥ 3 months	Discrete
Concurrent illnesses	Yes, No	Discrete

7.4. Status of Treatment Compliance

Analysis population(s): Safety analysis set

Analysis parameter: Presence or absence of receipt of a study drug injection

Analysis method: The number of subjects will be calculated for each number of injections(1, 2, 3, 4).

7.5. Efficacy Analyses

7.5.1. Primary endpoints

Analysis population(s): FAS

Analysis parameter: The anti-PRP antibody seroprotection (antibody titer ≥ 1 $\mu\text{g/mL}$) rate, and also the seroprotection rates for other antibodies (anti-diphtheria [REDACTED] anti-diphtheria [REDACTED] [REDACTED], anti-PT, anti-FHA, anti-tetanus, anti-poliovirus serotype 1, anti-poliovirus serotype 2, anti-poliovirus serotype 3)

Analysis method: For each analysis parameter, the number of subjects for each time point (4 weeks after the primary immunization, 4 weeks after the booster immunization), the number of subjects assessed for efficacy based on each antibody, the number of seroprotections, the seroprotection rate (%), and the two-sided, 95% confidence intervals will be calculated.

7.5.2. Secondary endpoints

7.5.2.1 Anti-PRP Antibody Seroprotection (titer ≥ 0.15 $\mu\text{g/mL}$) Rate

Analysis population(s): FAS

Analysis method: Anti-PRP antibody seroprotection (titer ≥ 0.15 $\mu\text{g/mL}$) rate

Analysis method: For each analysis parameter, the number of subjects at each time point (4 weeks after the primary immunization, 4 weeks after the booster immunization), the number of subjects assessed for efficacy, the number of seroprotections, the antibody seroprotection rate (%), and the two-sided, 95% confidence intervals will be calculated.

7.5.2.2 Antibody Titer Profiles

Analysis population(s): FAS

Analysis parameter: Titers of each type of antibody (anti-PRP, anti-diphtheria [REDACTED], anti-diphtheria [REDACTED], anti-PT, anti-FHA, anti-tetanus, anti-poliovirus serotype 1, anti-poliovirus serotype 2, anti-poliovirus serotype 3)

Analysis method: For each analysis parameter, the number of subjects by time point, the number of subjects assessed for efficacy, the geometric mean, the geometric standard deviation, the two-sided 95% confidence interval of the geometric mean, and the minimum, median, and maximum values will be calculated.

7.5.3. Issues in Statistical Analyses

7.5.3.1. Adjustments for Covariates

Not planned

7.5.3.2. Handling of Dropouts or Missing Data

Described in “5.1 Handling of Missing Values” of this document.

7.5.3.3. Interim Analyses and Data Monitoring

Not implemented

7.5.3.4. Multicenter Studies

Not planned

7.5.3.5. Multiple Comparison/Multiplicity

Not applicable

7.5.3.6. Use of an “Efficacy Subset” of Patients

Not implemented

7.5.3.7. Active-Control Studies Intended to Show Equivalence

Not applicable

7.5.3.8. Analyses of Subgroups

Not planned

7.6. Safety Analyses

7.6.1. Adverse Events

The adverse event terms will be reclassified based on MedDRA/J Version 20.0.

7.6.1.1. Adverse Event Incidences

Analysis population(s): Safety analysis set

Analysis parameter: Adverse events (solicited adverse events, immediate reactions, other), adverse drug reactions (solicited adverse events, immediate reactions, other), serious adverse events, serious adverse drug reactions, adverse events leading to discontinuation, adverse drug reactions leading to discontinuation

Analysis method: The number and proportion (and 95% confidence interval thereof) of subjects experiencing each type of event will be calculated.

7.6.1.2. Individual Adverse Events

Analysis population(s): Safety analysis set

Analysis parameter: Adverse events, adverse drug reactions, serious adverse events and reactions, adverse events and reactions leading to discontinuation

Analysis method: The numbers and proportions of subjects experiencing each type of event will be calculated by event category (solicited adverse events, immediate reactions, other) and by MedDRA/J SOC and PT. Additionally, adverse events and adverse drug reactions will be tabulated by event category (solicited adverse events, immediate reactions, other) and severity (mild, moderate, severe). If the same subject experiences the same event multiple times at different levels of severity, the event will be tabulated using the highest reported level of severity.

7.6.1.3. Incidence of Solicited Adverse Events by Number of Doses

Analysis population(s): Safety analysis set

Analysis parameter: Adverse events and reactions that are considered solicited adverse events

Analysis method: For each number of doses, and for each MedDRA/J SOC and PT, the numbers and proportions of subjects experiencing each type of event will be tabulated by event category (solicited adverse events, immediate reactions).

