17.5 Handling of e-Diary

Each subject's legal guardian will enter into the subject's e-Diary the information for the parameters specified in Section 9.2.4.1 every day until Day 14 after vaccination with the investigational product and also, as a rule, until the subject's symptoms have resolved for subjects who symptoms have not resolved by Day 14 after vaccination with the investigational product. The (sub)investigator or a clinical research coordinator will check the information that the subject's legal guardian entered into the e-Diary, and if there are any doubts about the information that has been entered, the investigator or clinical research coordinator will promptly confirm this information with the subject's legal guardian, and if there are any parts of the e-Diary that have not been filled out, will ask the subject's legal guardian to enter the symptoms to the extent possible.

In this study, of the safety assessment parameters, the presence or absence of vaccination site reactions, and the size or severity thereof, will be assessed based on the data that are entered into the e-Diary by the subject's legal guardian. Other adverse events will be assessed by the (sub)investigator based on both the information that has been entered into the e-Diary by the subject's legal guardian and the (sub)investigator's examination of the subject.

The principal investigator will store a copy of the e-Diary on a recording medium such as a CD-R provided by the study sponsor.

18. Direct Access to Source Documents

The principal investigator and the head of the study site will agree to cooperate with the monitoring and auditing of the study sponsor and the inspections of the institutional review board and regulatory authorities, and to provide these parties with direct access to all materials pertaining to the study.

19. Study Quality Control and Quality Assurance

The study sponsor must perform "study quality control" and "study quality assurance" based on Mitsubishi Tanabe Pharma's GCP Standard Operating Procedures, in order to maintain the quality and reliability of this study. In addition, the study sites and the principal investigators must cooperate with the study quality control and quality assurance activities of the study sponsor.

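### Does the by-dose table of solicited reactions count children who missed a dose, or have no diary for it, as reaction-free?

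*SAP*

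**What the plan says.** SAP 7.6.1.3 gives one population for the by-dose table, "Analysis population(s): Safety analysis set", and one instruction: "For each number of doses, and for each MedDRA/J SOC and PT, the numbers and proportions of subjects experiencing each type of event". It names no denominator.

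SAP 5.2 removes only two kinds of child from that set: "Subjects who did not take the investigational product at all" and "Subjects for whom absolutely no safety data are available following immunization with the investigational product". A child with one, two or three doses stays in, and so does a child who lacks a diary for a single dose.

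Three other SAP passages bear on the point:

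- Section 6.1 says of an assessment that was not performed that "this parameter will be handled as a missing value".
- Section 6.4 counts repeat events once within a period, and gives the period attached to each dose as an example.
- Section 7.4 states: "The number of subjects will be calculated for each number of injections(1, 2, 3, 4").

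Protocol 17.5 says that vaccination-site reactions "will be assessed based on the data that are entered into the e-Diary" by the guardian. Other adverse events are judged by the investigator from both the diary and the examination.

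**The concern.** Read literally, the named population doubles as the denominator. A child who stops after dose 2 would then sit in the dose 3 and dose 4 denominators without any chance of contributing a reaction. A child with no diary after a dose would look the same as a child who had no site reaction.

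Both effects push rates down. The dropout part can only build up over the course, and dose 4 comes 6 to 13 months after dose 3. Protocol sections 1(4) and 8.3.1 cite fewer local reactions as a feature of intramuscular injection, and Protocol 6.1 wants the data to support a look at differences from the subcutaneous study. An artificial fall in reactogenicity across doses, or against that study, would flatter the route under investigation.

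**Working it through.** **The plan's own figure.** SAP 2.4 gives an 83% chance of seeing a solicited event of 5.8% incidence among 30 children. Read as at least one child affected, 1 - (1 - 0.058)^30 = 0.8335, so the figure reproduces.

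**Does the SAP prescribe the whole safety set as divisor?** Four places help to decide.

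1. Population and denominator are separate things in this SAP. The efficacy sections name the FAS as the population, yet section 4.2 divides by the children with antibody results. Naming the safety set in 7.6.1.3 therefore does not fix the divisor.
2. Section 6.1 makes an unperformed assessment missing. Scoring an absent diary as no reaction would go against that, although the section does not mention diaries.
3. Section 6.4 works with a period for each dose. A child who never received dose 4 has no dose 4 period.
4. Section 7.4 yields the children by number of injections, and Tables 14.3.1.10 and 14.3.1.11 are organised by the same variable. The count needed for a per-dose divisor is already produced, though no sentence links the two.

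None of these states the denominator outright. Together they make the unfavourable reading the less natural one.

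**Size if the unfavourable reading were applied.** Let m be the number of the 30 children who did not receive, or were not observed after, a given dose. Then

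reported rate = true rate × (30 - m)/30.

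The documents give no value for m. The range 0 to 6 is an assumption.

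| m | factor | true 50% shown as | true 20% shown as |
|---|---|---|---|
| 0 | 30/30 = 1.000 | 50.0% | 20.0% |
| 1 | 29/30 = 0.967 | 48.3% | 19.3% |
| 3 | 27/30 = 0.900 | 45.0% | 18.0% |
| 6 | 24/30 = 0.800 | 40.0% | 16.0% |

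For precision, take 12 reactors (also an assumption) and Clopper-Pearson 95% limits, the method in SAP 7.1.3:

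- 12/30 = 40.0% (22.7 to 59.4)
- 12/27 = 44.4% (25.5 to 64.7)
- 12/25 = 48.0% (27.8 to 68.7)
- 12/24 = 50.0% (29.1 to 70.9)

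With no events, the upper limit is 11.6% for n = 30, 12.8% for n = 27 and 14.2% for n = 24.

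The shift for m = 3 is 44.4 - 40.0 = 4.4 percentage points. The interval at n = 30 is 59.4 - 22.7 = 36.7 points wide.

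**Could a reader detect the choice?** The table gives both a count and a proportion, so wherever the count is above zero the divisor can be recovered: 12/0.400 = 30, while 12/0.444 is about 27. Listings 16.2.3 and 16.2.5.1 show doses given and events by child.

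**The case for a change.** The strongest argument for a change is that the SAP writes out the antibody denominator in section 4.2 and has no matching sentence for safety. Section 7.4 shows that fewer than four doses is foreseen, but its counts are not tied to the by-dose table. The two tables carry only the safety-set label. The promise in section 5 to settle subject-handling rules before database lock is not itself a rule. Any error from the whole-set reading would run one way, and one sentence would close the gap.

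What stands is that the denominator is not written down, and that the whole-set reading would bias later-dose rates downward if children are lost.

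The rest is weaker:

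- **The rule itself.** No passage says that unexposed or unobserved children count as reaction-free.
- **Diaries.** Protocol 17.5 has staff ask guardians to fill gaps. Protocol 12.2 asks guardians of discontinued children who do not attend to complete the diary as far as possible. Missing diaries also need not become more frequent with dose number.
- **Direction.** The protocol's claim compares routes, not doses. No test is planned, and how the subcutaneous study tabulates its doses is not in these documents. The same convention in both could largely cancel.
- **The remedy.** Requiring a diary entry for every solicited reaction would conflict with Protocol 17.5. Systemic reactions also rest on the investigator's examination, so a child with investigator-recorded pyrexia and no diary would drop out along with a real event.

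**Conclusion.** The concern does not hold as a flaw in the plan. SAP 7.6.1.3 leaves its denominator unstated, and an analyst producing a table by injection number would ordinarily use the children who received that injection. Sections 6.1, 6.4 and 7.4 support that choice.

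The bias exists only if the analyst takes the other reading and some children miss a dose or go unobserved. It would then be a relative fall of m/30: none for m = 0, 3.3% for m = 1, 10% for m = 3 and 20% for m = 6. These values of m and the 12 reactors are illustrations, because the documents give no dropout, diary-completion or reaction rates.

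For an exploratory, descriptive study of 30 children, with counts shown beside proportions and listings by child, this is ordinary missing detail and no change is needed.

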5.2 Study Design

5.2.1 Study Design

Open-label, uncontrolled, multicenter study

The following investigational products will be administered.

- BK1310: A single dose of 0.5 mL (that contains 10 µg of Hib antigen as the oligosaccharide)

For the primary immunization, subjects will receive 3 doses of investigational product intramuscularly (into the thigh), 0.5 mL for each dose, at intervals of 3 to 8 weeks (standard vaccination interval: 4 weeks). For the booster immunization, subjects will receive a single dose of investigational product intramuscularly (into the thigh) at 6 to 13 months after the primary immunization. However, the repeated vaccination with investigational product at the same location as that which was used for the previous dose will be avoided.

Rationale

The amount of Hib antigen in the investigational product has been set at 10 µg through a comprehensive determination made on the basis of, among other information, the results obtained after the administration of the third dose of the investigational product in Cohort 1 (after the completion of the primary immunization) in ongoing study BK1310-J01.

Because there do not appear to be any major differences in immunogenicity or tolerability between

intramuscular administration and subcutaneous administration, this study has been designed as an exploratory, uncontrolled study.

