6.1 Target Sample Size

30 subjects as investigational product vaccinated subjects

Rationale

The sample size was set at 30 subjects who are eligible for inclusion in a stratified analysis for exploring the causes of any differences that may be found in efficacy or safety between intramuscular administration (this study) and subcutaneous administration (study BK1310-J01), based on the sample size that was used in the intramuscular administration study that was conducted for the vaccine that has already been approved (VaxemHIB aqueous suspension for injection).

Additionally, a simulation found that the probability of a solicited adverse event that has an incidence of 5.8% occurring in a single subject if the sample size is 30 would be 83%. The figure of 5.8% was chosen because this was the incidence of the least frequently reported solicited adverse drug reaction in the BK1310 group in the Japanese phase 2 study of MT-2301 (study MT-2301-J01).

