8.5 Concomitant Drugs/Therapies

8.5.1 Prohibited Concomitant Medication/Therapy

The concomitant use of the following drugs and therapies will be prohibited during the study periods (Visit 1 through Visit 6).

- (1) Hib, pertussis, diphtheria, tetanus, or polio vaccines other than the investigational products
- (2) Immunoglobulin preparations
- (3) Corticosteroids at prednisolone equivalent doses of 2 mg/kg/day or higher (except for topical drugs)
- (4) Immunosuppressants (except for topical drugs)
- (5) Blood transfusions
- (6) Immunosuppressant therapies
- (7) Investigational products other than BK1310

The concomitant use of the following drugs will be prohibited from 27 days before until 14 days after the vaccination with investigational product.

- (8) Live vaccines (e.g., BCG, measles, rubella, mumps, varicella, rotavirus*)

*: Simultaneous vaccination with the investigational product will be permitted only for a rotavirus vaccine

The concomitant use of the following drugs will be prohibited from 6 days before until 14 days after the vaccination with investigational product.

(9) Inactivated vaccines (e.g., Pneumococcal,** influenza, Japanese encephalitis, hepatitis A, hepatitis B**)

**: Simultaneous vaccination with the investigational product will be permitted only for the pneumococcal and hepatitis B vaccines. The site of vaccination will be the arm or the thigh on the side opposite that used to administer the investigational product.

Rationale

(1) This criterion was established because of the potential effects on the assessments of efficacy.

(2)(5) These criteria were established because of the potential effects on the assessments of efficacy, since they might contain antibodies to the active ingredients of the investigational drug.

(3)(4)(6) These criteria were established because of the potential effects on the assessments of efficacy and safety, since these drugs could suppress immune function.

(7) This criterion was established because of safety and ethics considerations.

(8)(9) These criteria were established because of safety and ethics considerations, in accordance with the vaccination intervals for other vaccines described in the Routine Immunization Guidelines. It was also decided that the concomitant use of other vaccines should be prohibited up until 14 days after vaccination with the investigational product in order to check the effects on safety of combining the vaccines.

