9.2.2 Vaccination Status

The (sub)investigator or a clinical research coordinator will record the following information in the case report form.

- (1) Day of vaccination with investigational product
- (2) Body temperature (axillary) prior to vaccination with the investigational product
- (3) Site of vaccination with the investigational product
- (4) Status of simultaneous immunization with a vaccine other than the investigational product (day of vaccination, type of vaccine simultaneously administered, site of vaccination)

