For events other than vaccination site reaction, which are pre-specified adverse events, the (sub)investigator will assess whether or not there is a “reasonable possibility” that the investigational product caused the adverse event in question. This assessment is made in consideration of the underlying disease, concomitant medical diseases, and other aspects of the natural course of the primary disease, concomitant therapies risk factors and factors other than the investigational product, and the temporal relationship between investigational product dosing and adverse event onset. If it is unknown or cannot be determined whether or not there is a reasonable possibility, then it will be concluded that there is a reasonable possibility. For all vaccination site reactions (vaccination site redness, swelling, induration, and pain), which are pre-specified adverse events, the causal relationship to the investigational product will be classified as “there is a reasonable possibility.” Adverse events for which it is thought “there is a reasonable possibility” of there being a causal relationship with the investigational product are considered adverse drug reactions.

1. Reasonable possibility
2. No reasonable possibility

5) Outcome

The outcomes of adverse events will be classified using the following 6 categories.

1. Recovered
2. Recovering
3. Did not recover
4. Recovered, but with sequelae
5. Death
6. Unknown

6) Day of outcome

The day of outcome will be classified according to the following criteria.

Recovered	: The day of resolution. However, if the day on which the subject recovered cannot be identified, then the day of outcome will be the day on which the outcome was confirmed or determined.
Recovering	: The day on which it was confirmed or determined that the subject was recovering.
Did not recover	: The day on which it was confirmed or determined that the subject had not recovered.

Recovered with sequelae	: The day on which it was confirmed or determined that sequelae were present.
Death	: The day of death. However, if the day of death cannot be determined, then this will be the day on which the death was confirmed or determined.
Unknown	: The day of death if the subject died due to a cause other than the adverse event in question and the outcome was unknown. Otherwise, this will be the day on which the outcome was confirmed or determined.

7) Follow-up

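### Systemic reaction rates may include reactions to same-day vaccines, and the SAP never uses the co-vaccination data that the case report form records

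*SAP*

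**What the plan says.** Protocol 5.2.1 describes the design as "Open-label, uncontrolled, multicenter study", and 6.1 sets the size at "30 subjects as investigational product vaccinated subjects".

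Protocol 8.5.1 restricts other vaccines around each dose, up to 14 days afterwards, partly so that the safety of combining vaccines can be examined. Same-day use is exempt: "Simultaneous vaccination with the investigational product will be permitted only for the pneumococcal and hepatitis B vaccines" among inactivated vaccines, and rotavirus among live ones. Protocol 9.2.2 requires the case report form to hold the "Status of simultaneous immunization with a vaccine other than the investigational product (day of vaccination, type of vaccine simultaneously administered, site of vaccination").

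Protocol 9.2.4.2 treats a local reaction at another vaccine's site as an ordinary adverse event, outside the pre-specified category. It has no matching rule for the systemic reactions, which count as pre-specified through Day 14 whatever else was injected that day. For these the investigator assesses causality and weighs other factors, but "If it is unknown or cannot be determined whether or not there is a reasonable possibility, then it will be concluded that there is a" possible causal link, which makes the event an adverse drug reaction.

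SAP 7.6.1.1 and 7.6.1.2 summarise events overall, by SOC and PT, and by severity. SAP 7.6.1.3 adds dose number: "For each number of doses, and for each MedDRA/J SOC and PT, the numbers and proportions of subjects experiencing each type of event will be" set out by event category. The output list in SAP 11 has no table that uses same-day vaccination.

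Protocol 6.1 and SAP 2.4 justify the sample size partly by a stratified analysis to explore why efficacy or safety might differ between the intramuscular and subcutaneous routes. The SAP specifies no stratified analysis, and SAP 9 reports no change from the protocol.

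**The concern.** The protocol recognises that another vaccine given close to BK1310 can blur the safety reading, and it deals with this for local reactions by site. For systemic reactions that device does not work: a fever after two injections on one day has no site. The one piece of information that would help a reader, whether another vaccine was given with that dose, is collected and then left out of every planned summary table.

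Safety is half of the study objective, and no comparator arm shares the co-vaccine contribution. Without knowing how many doses were co-administered, a reader cannot tell whether a systemic rate describes BK1310 mostly alone or mostly together with other vaccines. If a difference from the subcutaneous study appears, same-day vaccination is one candidate explanation that the recorded data could help to examine, and the SAP makes no provision for it.

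**Working it through.** **The plan's own figure.** Protocol 6.1 takes "a solicited adverse event that has an incidence of 5.8" per cent and gives the probability of it "occurring in a single subject if the sample size is 30 would be 83" per cent. Reading this as at least one subject, 1 − (1 − 0.058)^30 = 0.833, so the figure reproduces. (Exactly one subject would give 30.8%.) It is not in dispute, and it says nothing about same-day vaccines.

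**Is the co-vaccination information used?** Setting the sections side by side:
- permitted: Protocol 8.5.1, identically for all four doses;
- recorded: Protocol 9.2.2, with day, type and site;
- separated for local reactions: yes, by site (Protocol 9.2.4.2);
- separated for systemic reactions: no;
- used in SAP 7.6.1.1 to 7.6.1.3 or in the tables of SAP 11: no.

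SAP 7.5.3.8 says that subgroup analyses are not planned, but it sits in the efficacy part. The firmer evidence is that 7.6 itself plans no such split.

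**How large could the effect be?** The documents give no inputs for this, so all three below are assumptions:
- p0 = per-dose rate of a systemic reaction with BK1310 alone, 10% to 30%;
- c = share of doses given with a same-day vaccine, 25% to 90%;
- q = independent added risk from that vaccine, 10% to 30%.

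Rate with a same-day vaccine = 1 − (1 − p0)(1 − q). Pooled rate = p0 + c·q·(1 − p0). Excess over BK1310 alone = c·q·(1 − p0).

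| p0 | c | q | With same-day vaccine | Pooled | Excess |
|---|---|---|---|---|---|
| 30% | 25% | 10% | 37% | 31.75% | 1.75 points |
| 20% | 50% | 20% | 36% | 28% | 8 points |
| 20% | 75% | 20% | 36% | 32% | 12 points |
| 10% | 90% | 30% | 37% | 34.3% | 24.3 points |

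The first and last rows are the extremes of the assumed grid: 0.25 × 0.10 × 0.70 = 0.0175 and 0.90 × 0.30 × 0.90 = 0.243. The formula also assumes that p0 is the same in children who do and do not receive another vaccine.

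**What could a split show at this sample size?** With Clopper-Pearson intervals, as SAP 7.1.3 specifies:
- pooled, 9/30 = 30.0% (95% CI 14.7 to 49.4);
- with, 6/15 = 40.0% (16.3 to 67.7);
- without, 3/15 = 20.0% (4.3 to 48.1).

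If 90% of doses were co-administered, about 30 × 0.10 = 3 children per dose would be unexposed. Zero events in 3 has an upper limit of 1 − 0.025^(1/3) = 70.8%.

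**The case against.** The strongest reply is that the plan already answers a legitimate question. The study is exploratory, runs no tests, and aims to confirm safety in the clinical setting. A systemic rate under the co-vaccination that the protocol permits is a reasonable target, and a split of 30 infants, not randomised and possibly tied to age and dose number, would not give a BK1310-alone rate. The 4 × 30 = 120 dose records are repeated measures on the same children. All of this stands. It limits the request to description and accurate labelling; it does not explain why the recorded data appear in no summary table.

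A reader might infer that the solicited-event tables credit other vaccines' reactions to BK1310. They do not: adverse events are counted regardless of causality. Attribution enters only through the adverse drug reaction tables, where the investigator must first consider concomitant therapies and other factors. The default applies only when the cause cannot be determined, and the documents do not show how often that will be.

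A reader might also infer that the by-dose table is confounded because co-vaccination differs between the primary series and the booster, or that the mix differs from study BK1310-J01. The documents show neither. They give no frequency of same-day vaccination at any dose, and nothing about same-day vaccination in J01 apart from its ActHIB and TETRABIK comparator.

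Finally, the planned listings of adverse events, study drug administration and concomitant medications could support case-by-case reading. The SAP does not say whether same-day vaccines appear in them, and a listing is not a summarised rate.

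**Conclusion.** The point holds in a limited form. Same-day vaccines are permitted and recorded, systemic reactions cannot be assigned by site, and no planned safety table uses the record. Systemic adverse event rates, and adverse drug reaction rates where cause is undetermined, may therefore contain reactions to other vaccines. Local reaction rates at the BK1310 site are not the issue.

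The size in this trial cannot be known from the documents. The range of about 2 to 24 percentage points per dose rests wholly on the assumed values of p0, c and q, and it shrinks towards zero as the share or the added risk falls. A narrower figure is easy to produce but no better founded: fixing a 20-point gap and shares of 50% to 90% gives 10 to 18 points (0.5 × 20 and 0.9 × 20), which only restates the assumptions.

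The stratified analysis in the sample-size rationale strengthens the case modestly. It names safety differences between routes as something to explore, although neither document says that co-vaccination would be a stratum. This is a cheap improvement to the reporting, not a flaw that undermines the study.

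**What to change.** Amend SAP 7.6.1.3 and the output list in SAP 11:

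1. For each dose, report the number of subjects who received a simultaneous vaccine, and its type.
2. Tabulate the systemic solicited events (pyrexia, irritability, crying, and the appetite and sleep terms) by dose, separately for doses given with and without a simultaneous vaccine, once for adverse events and once for adverse drug reactions. State that this is description only, with no tests and no claim to isolate a BK1310 effect.
3. Label the pooled systemic rates in 7.6.1.1 to 7.6.1.3 *BK1310 with or without simultaneous vaccines*.

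The cost is a small amount of programming on data already in the case report form, with no new collection and no change to the conduct of the study. The downside is small cells and possibly a near-empty stratum. Item 1 would show that directly, and a reader needs to know it to interpret the pooled rate.
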